11.3.2 Packaging and Labeling

Trial medication and CGM Freestyle Libre 2 will be dispensed by Curexa Pharmacy [name], United States.

11.3.3 Storage

Tablets should be stored at room temperature, away from heat and light. Tablets are dispensed in a tight, light-resistant labeled container.

11.4 Concomitant Medications

If participants fit eligibility criteria but are on other medications, they should continue to take those at the prescribed dosages. They will be instructed to tell their other physicians, medical providers, and pharmacists of their enrollment in the trial. Any changes to concomitant medications or any planned surgery should be discussed with the PI immediately.

12 Adverse Event Reporting

12.1 Adverse Events Definitions

Adverse drug reaction (ADR): a noxious and unintended reaction to a drug at doses normally used in humans for prophylaxis, diagnosis, therapy of diseases, or for the modification of physiological function where a causal relationship is at least reasonably possible.

Adverse event (AE): an adverse occurrence experienced by a study subject during the course of the clinical trial that is not necessarily associated with the drug. An AE can, therefore, be any unfavorable and unintended sign (including an abnormal laboratory finding), symptom, or disease temporally associated with the use of the investigational product, whether or not related to the investigational product. When an AE has been determined to be related to the investigational product, it is considered to be an adverse drug reaction.

12.2 Serious Adverse Events

Serious adverse events (SAE): any AE that results in death, is life-threatening, requires inpatient hospitalization, is persistent, or causes significant disability/incapacity, or causes a congenital anomaly or birth defect.

Adverse events will be graded according to the system below:

1. Grade 1: Asymptomatic or mild symptoms; clinical or diagnostic observations only; no intervention indicated (e.g. headache, nausea, abdominal discomfort).
2. Grade 2: Moderate; minimal, local or noninvasive intervention (e.g. vomiting, diarrhea, shortness of breath).
3. Grade 3: Severe; or medically significant but not immediately life threatening; hospitalization or prolongation of hospitalization indicated; disabling (e.g. dehydration, hypotension).
4. Grade 4: Life-threatening ; urgent intervention indicated (e.g. respiratory failure, myocardial infarction, liver failure).
5. Grade 5: Death related to an AE.

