6.4 Rationale and Hypothesis

Canagliflozin is a prime candidate to reduce glucose spikes and blood sugar. It has consistently acted to treat type 2 diabetes and has been shown to improve biomarkers such as fasted glucose and glucose spikes.

The current FDA-approved use of the drug is for use together with diet and exercise to treat type 2 diabetes. Canagliflozin is sometimes used in combination with insulin or other diabetes medications taken orally. It is routinely prescribed at equal or higher doses than the ones proposed in this trial.

AgelessRx Trial doses: 100 mg and 150 mg doses, taken every day and every-other day, respectively.

FDA-approved dose: Maximum recommended dose: 300 mg once daily.

Some possible side effects at the FDA-approved doses include hypoglycemia, indigestion, nausea, UTI, increased urination or thirst, hypotension, ketoacidosis, dehydration, and headache. The doses we propose have potential for some side effects, though the drug is generally well tolerated.

This trial will use a lower dose than the maximum one recommended by the FDA. We are using a maximum of 150 mg in one day vs the maximum of 300 mg each day recommended by the FDA. At this smaller dose, side effects are less common⁸. This dose has been shown to be generally safe.

Our hypothesis is three-fold:

1. Canagliflozin can be used safely and is well tolerated at doses of 100 mg per day or 150 mg every two days in healthy, non-diabetic individuals.
2. Usage of canagliflozin at these doses can effectively reduce glucose spikes (and their detrimental effects) and blood sugar levels measured by CGM in a healthy population.
3. Usage on alternate days will be effective as measured by our endpoints.

7. Objectives

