12.3.2 Expedited

Serious adverse events that occur while the research participant is actively participating in the research study will be reported to the IRB within 48 hours for the duration of the study (until study is closed at the IRB).

13 Statistical Analysis

Demographic and baseline characteristics will be summarized using descriptive statistics. Blood tests will be analyzed using analysis of variance. Evaluation will be performed by research and medical teams.

14 Ethics

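### The SAE definition in 12.2 has no limb for medically significant events, although the protocol's own Grade 3 names them, so some severe events carry no 48-hour IRB report

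*Combined protocol and SAP*

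**What the plan says.** Section 12.2 defines an SAE as "any AE that results in death, is life-threatening, requires inpatient hospitalization, is persistent, or causes significant disability/incapacity", and adds a last limb for congenital anomalies and birth defects. That is a closed list of six limbs.

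The same section then sets out a five-grade severity scale. Grade 3 covers events that are severe, or "medically significant but not immediately life threatening; hospitalization or prolongation of hospitalization indicated", or disabling, and it gives dehydration and hypotension as examples. Grade 4 is separate: "Life-threatening ; urgent intervention indicated".

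Two reporting duties depend on whether an event is an SAE:

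- Section 12.3.2: "Serious adverse events that occur while the research participant is actively participating in the research study will be reported to the IRB within 48 hours".
- Section 12.3.1: participants are asked to tell the Principal Investigator (PI) at once about any SAE.

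For all other adverse events, 12.3.1 has the PI notified, collects information through monitoring forms and has it entered in the medical record. It also says that expected and unexpected events will be reported, but names no recipient and no deadline.

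Section 6.4 lists possible side effects at the approved doses, including hypoglycaemia and "hypotension, ketoacidosis, dehydration, and headache".

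**The concern.** The severity scale recognises two kinds of event that the SAE definition in the same section leaves out: the medically significant event that does not threaten life, and the prolonged hospital stay. Because both urgent reporting duties hang on the SAE definition and no grade triggers either of them, an event can be Grade 3 on the protocol's own scale and still carry no reporting clock.

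This matters more here than in a trial with clinic visits. The trial is run entirely by telemedicine (title page), no data monitoring committee is described, and section 11.3.1 has dose changes or discontinuation for adverse events discussed in a call with the Research Coordinator. The 48-hour report is the only expedited outside check in the document. Section 14.2 stresses to participants that they can expect no benefit. Safe use and good tolerability form the first hypothesis in 6.4, and section 10.3 makes safety and tolerability a secondary endpoint.

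**Working it through.** No figure in the plan is at stake, so the check sets the texts side by side.

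**Step 1. Grade 3 against the SAE list (both in 12.2).**

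| Element of Grade 3 | Counterpart in the SAE list |
|---|---|
| Severe | None; severity and seriousness are separate scales, so none is needed |
| Medically significant, not immediately life-threatening | None |
| Admission indicated | Inpatient admission required (close match) |
| Hospital stay prolonged | None |
| Disabling | Significant disability or incapacity (close match) |

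Two elements that ordinarily bear on seriousness, medical significance and prolongation, have no counterpart.

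**Step 2. Trace one event through the six limbs.** Take a medically significant episode of dehydration or hypotension, graded 3, treated without admission, resolving promptly and leaving no disability.

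| SAE limb | Met? |
|---|---|
| Death | No |
| Life-threatening | No (that would be Grade 4) |
| Inpatient admission required | No |
| Persistent | No |
| Significant disability or incapacity | No |
| Congenital anomaly or birth defect | No |

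It meets 0 of 6 limbs, so it is not an SAE. Section 12.3.2 does not require a 48-hour report, and the request for immediate reporting in 12.3.1 does not cover it.

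**Step 3. Neighbouring events.** A Grade 4 episode is an SAE without admission. An episode that needs admission, or is disabling, is also an SAE. Read literally, persistence is a limb of its own, so a mild but lasting complaint is an SAE while the short severe episode in step 2 is not.

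**Step 4. Does any other text restore the missing limbs?**

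- Section 12.1 defines adverse events and adverse drug reactions, not seriousness.
- Section 12.3.1 cites regulations for how adverse events are documented. Their text is not in the document, so they cannot supply a limb.
- Appendix E says that the ethics committee must receive information on SAEs but does not define the term.
- Section 13 describes no safety summary and no classification rule.

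Nothing restores them.

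**Step 5. After the change.** With a limb for a medically significant event as judged by the PI, the event in step 2 can be classified as an SAE. The duties in 12.3.1 and 12.3.2 then apply.

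**The case against.** The strongest case on the other side has four parts.

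*The gap is narrow.* Life-threatening, disabling and persistent events and those needing admission are already SAEs. This stands. A reader might infer that any severe ketoacidosis or hypoglycaemia treated in an emergency department would escape the 48-hour rule. The documents do not support that: neither event is graded anywhere, and such an episode could well be judged life-threatening, which makes it an SAE without admission. The documents also leave open whether an event for which admission was judged necessary but did not happen counts as requiring admission. The safer examples are dehydration and hypotension, which the protocol itself places at Grade 3.

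*Nothing is hidden.* This also stands. The PI is notified of every adverse event, section 8.1 provides seven daily side-effect surveys during dosing, and the safety endpoint in 10.3 rests on adverse-event reporting, not on an SAE count. Nothing bars the PI from informing the IRB voluntarily. A reader might infer that Grade 3 events would be lost, or that zero SAEs alongside Grade 3 events is in itself an error. Neither follows, since severity and seriousness are different scales.

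*Prolongation hardly matters here.* Largely true. It needs a participant already in hospital for another reason, such as the planned surgery mentioned in 11.4, during about two weeks of participation.

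*No numerical effect can be shown.* True. It is tempting to count how many of the side effects in 6.4 could reach Grade 3 without admission, or to note that one participant in an arm of 10 is 1/10 = 10%. The first is clinical judgement that the documents do not supply, and the second is only the size of the arm. Neither estimates how many events would be missed. Section 6.4 also says that side effects are less common at the lower dose.

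What remains is that a definite class of event, which the protocol itself regards as medically significant, has no expedited route.

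**Conclusion.** The point holds in a limited form. As written, 12.2 and 12.3 do not require a 48-hour IRB report, or an immediate report from the participant, for an event that is severe or medically significant but is not life-threatening, not disabling, not persistent and not in need of admission. Dehydration and hypotension, as Grade 3 examples in 12.2 and possible drug effects in 6.4, are cases in point. The omission of prolonged hospitalisation is a lesser part of the same mismatch.

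The loss is expedited reporting and classification as serious; awareness by the PI and capture in the adverse-event data remain. No expected number of affected events can be given.

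The conclusion assumes that the six limbs are the whole definition and that the PI applies them as written. It rests on the mismatch within the document, not on any outside standard for what an SAE definition must contain. It is a cheap change worth making before enrolment.

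**What to change.** Reconcile the SAE list in 12.2 with the Grade 3 text and with 12.3.2:

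1. Add two limbs to the definition in 12.2: *or prolongs existing hospitalization*, and *or is judged by the Principal Investigator to be a medically significant event*.
2. Do not make every Grade 3 event serious by definition. Grade 3 also covers events that are merely severe, so that rule would merge severity with seriousness and go beyond the gap.
3. Leave 12.3.1 and 12.3.2 as they are; both then apply to the added events.
4. Add a sentence to section 13 that SAEs will be summarised by arm on the revised definition, since no such summary is described now.

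The cost is two phrases in 12.2, one sentence in section 13 and possibly one or two more expedited IRB reports among at most 20 participants. The second limb brings some PI judgement into the classification, so the reason for each decision should be recorded.

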12.3 Reporting of Adverse Events

12.3.1 Routine

The principal investigator will be notified about any adverse events. Furthermore, this information will be obtained through monitoring forms sent out to participants.

The Principal Investigator will document this information in the participant's medical record. Participants will be asked to report any serious adverse event immediately to the Principal Investigator. This can be done by email or phone (after hours phone number is available).

AEs will be documented using standard AE reporting (FDA regulations 21CFR314.80 and 21CFR213.32(s)). Both expected (already known) and unexpected AEs will be reported.

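### As worded in section 12.2, persistence alone makes an adverse event serious, so mild lasting effects could be counted and expedited as SAEs

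*Combined protocol and SAP*

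**What the plan says.** Section 12.2 gives the protocol's only definition of a serious adverse event: "any AE that results in death, is life-threatening, requires inpatient hospitalization, is persistent, or causes significant disability/incapacity", followed by congenital anomaly or birth defect. The same section then sets out a five-level severity scale, whose lowest level is "Grade 1: Asymptomatic or mild symptoms; clinical or diagnostic observations only; no intervention indicated". Headache and nausea are among its examples.

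Section 12.1 casts the net for an adverse event widely: "any unfavorable and unintended sign (including an abnormal laboratory finding), symptom, or disease temporally associated with the use of the investigational product". A causal link to the drug is not required.

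Two duties hang on the SAE label. Under section 12.3.1, "Participants will be asked to report any serious adverse event immediately to the Principal Investigator". Under section 12.3.2, SAEs that arise during active participation "will be reported to the IRB within 48 hours".

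Section 6.4 names possible side effects at the approved doses: "hypoglycemia, indigestion, nausea, UTI, increased urination or thirst, hypotension, ketoacidosis, dehydration, and headache". It gives no frequency or duration for any of them.

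**The concern.** In the section 12.2 list, persistence has its own verb and its own place between commas. Disability or incapacity comes after it, with a different verb. Read as a rule, the sentence makes any adverse event serious if it persists, however mild it is.

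That matters because the sentence is operative: it decides what is reported at once to the investigator and what goes to the IRB on a 48-hour clock. Staff would have two choices. They could follow the text and expedite mild lasting symptoms as SAEs, or they could depart from it with no written rule for doing so. Persistence is not defined, so two assessors could classify the same symptom differently. Adverse event reporting is one component of the secondary safety and tolerability endpoint in section 10.3. In a trial of at most 20 people, a few classifications would change how the safety data look.

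**Working it through.** The plan states no SAE figure, so there is nothing to reproduce. The check is a reading of the text, followed by an illustration of size.

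**Step 1. Does anything in the protocol limit persistence?**

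- *Adverse event definition (12.1).* It admits any unfavorable sign or symptom, related or not. It does not exclude mild events.
- *Severity grades (12.2).* They rate severity and set no minimum grade for an SAE. A Grade 1 event is not ruled out.
- *Duration.* No threshold is given. Treatment lasts 7 days (Synopsis), and section 8.1 plans 7 daily surveys of side effects. A mild symptom recorded on successive days could be called persistent, or not, depending on the assessor.
- *Routine reporting (12.3.1).* It cites federal regulations for documenting adverse events. It does not say that they replace the section 12.2 definition.
- *Statistical analysis (13).* It does not mention adverse events.

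Nothing narrows the criterion. As written, a Grade 1 event that persists is an SAE.

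**Step 2. How many extra SAE cases could follow?**

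Inputs: n = 20, the maximum enrolment (Synopsis; sections 8.3 and 9.1), and n = 10 per arm (Synopsis). The share p of participants with a mild adverse event that an assessor would call persistent is **assumed**, because the documents give no value. Participants are taken as independent, and each is counted once.

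- Expected cases = n × p
- Chance of at least one case = 1 − (1 − p)^n

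| Assumed p | Expected cases, n = 20 | Chance of at least one, n = 20 | Chance of at least one, n = 10 |
|---|---|---|---|
| 2% | 0.4 | 33% | 18% |
| 5% | 1 | 64% | 40% |
| 10% | 2 | 88% | 65% |
| 20% | 4 | 99% | 89% |
| 30% | 6 | 99.9% | 97% |

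Example: at p = 10% and n = 20, 20 × 0.10 = 2 expected cases, and 1 − 0.90^20 = 1 − 0.122 = 0.878.

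If persistence is read as describing disability or incapacity, the same mild events give no SAEs at any p.

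**Step 3. Hospitalization criterion.** The SAE definition covers an event that requires admission. The Grade 3 text in the same section also names a lengthened hospital stay. An event that only prolongs a stay is therefore covered by the grading text and not listed in the SAE definition.

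**The case against.** The strongest reply is that this is a drafting slip. Persistence was probably meant to describe disability, and an experienced assessor may read it that way. The error also runs toward over-reporting, so no serious event is missed through this phrase. All adverse events already go to the investigator, and each is graded, so a mild event would remain visible as Grade 1. The size is an assumption multiplied by a ceiling of 20, and section 6.4 says that side effects are less common at the lower dose.

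Much of this stands, and it keeps the point minor. It does not remove the point. The slip sits in the only rule that decides what is expedited, and the text nowhere says that the narrower reading is intended.

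A reader might infer more than the documents support:

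- *That the trial's SAE rate will be wrong.* No SAE rate is reported, defined as an endpoint or planned for analysis.
- *That the SAE count is the main safety result.* Section 10.3 measures safety through adverse events, blood pressure and tolerability surveys, and does not single out SAEs.
- *That expedited reporting would be overwhelmed.* Even the top of the assumed range is about 6 cases in a study planned to last at most 90 days.
- *That increased urination or thirst will become an SAE.* This depends on an undefined term and on a duration that the protocol does not give. Only *could* is supportable.

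**Conclusion.** The wording is wrong as a classification rule, and the point holds at minor severity. Taken literally, section 12.2 lets a lasting event with "Asymptomatic or mild symptoms; clinical or diagnostic observations only; no intervention indicated" qualify as an SAE. Assessors may also apply the criterion inconsistently.

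The range of 0.4 to 6 extra cases rests wholly on the assumed share of 2% to 30%, on full enrolment of 20, and on assessors treating those mild effects as persistent. It is an illustration and not a forecast.

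The consequence is confined to expedited reporting and to the adverse event reporting that feeds the secondary safety endpoint. The primary glucose endpoint and the sample size are unaffected, and the plan contains no power calculation that could change. The gap on prolonged hospitalization is a real inconsistency within section 12.2, but no effect of it can be shown in this decentralized study.

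**What to change.** Amend the definition in section 12.2:

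1. Reword the criterion so that persistence describes the disability, for example: *causes persistent or significant disability/incapacity*.
2. Add that seriousness is judged separately from the severity grade.
3. As a consistency point, reconcile the hospitalization criterion with the Grade 3 text on prolonged stays.

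The cost is a short protocol amendment communicated to the IRB under section 15.1. It needs no new data, participants or analyses. It is best made before any event is classified; events already classified should be checked again under the reworded definition.

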12.3 Reporting of Adverse Events

12.3.1 Routine

The principal investigator will be notified about any adverse events. Furthermore, this information will be obtained through monitoring forms sent out to participants.

The Principal Investigator will document this information in the participant's medical record. Participants will be asked to report any serious adverse event immediately to the Principal Investigator. This can be done by email or phone (after hours phone number is available).

AEs will be documented using standard AE reporting (FDA regulations 21CFR314.80 and 21CFR213.32(s)). Both expected (already known) and unexpected AEs will be reported.

12.3.2 Expedited

Serious adverse events that occur while the research participant is actively participating in the research study will be reported to the IRB within 48 hours for the duration of the study (until study is closed at the IRB).

13 Statistical Analysis

Demographic and baseline characteristics will be summarized using descriptive statistics. Blood tests will be analyzed using analysis of variance. Evaluation will be performed by research and medical teams.

14 Ethics

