Objectives: Primary: To measure the effects that canagliflozin intervention has on reducing average glucose in healthy individuals. Secondary: To assess the tolerability and side effects and urinary glucose excretion following the pulsatile dosing protocol.
Methodology: 
1. Candidates will be offered participation through word of mouth and AgelessRx platform.2. Once screened and enrolled, participants will be randomized into one of two arms (A and B) and provided with all items included in the materials list below.3. Arms A & B:
a Day 0: Participants will attach a continuous glucose monitor (CGM) and follow instructions for calibration period.b Day 1 – 14: Participants will take morning blood pressure readings, and keep dietary intake journal via Lifesum.c Day 7: Participant completes Urine Collection Kit #14. Arm A:
a Day 8 - 14: Participants take 100mg Invokana (canagliflozin) with first meal daily.b Day 15: 24h after final dose, Participant completes Urine Collection Kit #2c Day 16: 48h after final dose, Participant completes Urine Collection Kit #3d Day 17: 72h after final dose, Participant completes Urine Collection Kit #45. Arm B:
a Day 8 - 14: Participants take 150mg Invokana (canagliflozin) with first meal daily, every other day for a total of 4 doses.b Day 15: 24h after final dose, Participant completes Urine Collection Kit #2c Day 16: 48h after final dose, Participant completes Urine Collection Kit #3d Day 17: 72h after final dose, Participant completes Urine Collection Kit #4
Number of subjects planned: Up to 20 healthy individuals via telehealth administration, 10 individuals in each Arm.

Diagnosis and main criteria for inclusion: Subjects will be healthy and of any sex, any ethnicity, and any age from 18-85. Participants must be approved by AgelessRx Medical Team for use of canagliflozin. They also require a CGM-compatible mobile device ([defined here](#))

Test product, dose, and mode of administration (proposed): The tablets will be from the brand Invokana and have a dosage of 100 mg or 300 mg per tablet. Investigational drugs are to be administered orally. Investigational drugs will be provided by Curexa Pharmacy, [name]

Duration of treatment: 7 days

Criteria for evaluation:

Efficacy:

- CGM data
- Urinary glucose

Safety:

- Tolerability

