- Adverse events
- Blood pressure

Statistical analysis: Demographic and baseline characteristics will be summarized using descriptive statistics. CGM readings will be analyzed using analysis of variance. Evaluation will be performed by research coordinators/MDs.

3. Study Design

[figure not shown]

Table of Contents

1. Signature Page	2
2. Synopsis	3 - 4
3. Study Design	5
4. Table of Contents	6 - 7
5. List of Abbreviations	7
6. Background and Rationale	8
6.1. Glucose Spikes	8
6.2. Canagliflozin	8
6.3. Current standard of care and alternative treatments for reduction of glucose spikes	9
6.4. Rationale and Hypothesis	9
7. Objectives	9 - 10
7.1. Primary Objective	9
7.2. Secondary Objective	10
8. Experimental plan	10
8.1. Study Design	10
8.2. Cost of Participation	10
8.3. Number of Centers and Subjects	10
8.4. Estimated Study Duration	10
9. Subject Selection	10
9.1. Number of Subjects	10
9.2. Inclusion Criteria	10
9.3. Exclusion Criteria	11
9.4. Withdrawal	11
10. Schedule of Assessments and Procedures	11
10.0. Patient Recruitment	11
10.1. Screening	11
10.2. Enrollment	11
10.3. Safety and efficacy evaluations	11
11. Investigational Product	12

11.1. Investigational Drug	12
11.2. Control Drug	12
11.3. Dosing and Administration	12
11.3.1. Dose Escalation, Dose Adjustments, Stopping Rules	12
11.3.2. Packaging and Labelling	12
11.3.3. Storage	12
11.3.4. Accountability	12
11.4. Concomitant Medications	12
12. Adverse Event Reporting	12
12.1. Adverse Events Definitions	13
12.2. Serious Adverse Events	13
12.3. Reporting of Adverse Events	13
12.3.1. Routine	13
12.3.2. Expedited	13
13. Statistical Analysis	13
14. Ethics	14
14.1. Ethical Conduct of the Study	14
14.2. Participant Information and Consent	14
14.3. Study Participant Confidentiality	14
15. Administrative Procedures	14
15.1. Modifications to the Protocol	14
15.2. Plans for Dissemination of Findings	14
16. Reference List	15
Appendix	16
Appendix A	16
Appendix E	18

5. List of Abbreviations

Abbreviation	Definition
ADR	Adverse Drug Reaction
AE	Adverse event
SAE	Serious Adverse event
CGM	Continuous Glucose Monitor

6. Background and Rationale

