7.1 Primary Objective

To measure the effects that Canagliflozin intervention has on blood glucose at the tested doses. This will be measured by observing glucose spikes following a high-carbohydrate meal at the tested doses, as well as by studying baseline glucose levels with and without canagliflozin.

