8.1 Study Design

This study is designed to mitigate the effects of glucose with intermittent oral Canagliflozin for healthy, non-diabetic volunteers of any sex who enroll in the study. The volunteers can be within 18-85 years of age at the time of enrollment. Participants will provide informed consent via AgelessRx EMR. If eligible, prescriptions will be provided online through the AgelessRx website (www.agelessrx.com). Participants will be randomized into two arms: Arm A will take 100 mg of canagliflozin each day for a total of 7 doses, while Arm B will take 150 mg of canagliflozin every other day for a total of 4 doses. Participants in Arm B will also be provided a pill cutter to use throughout the trial on the 300mg tablet.

All participants will begin the trial on the day that they apply a continuous glucose monitor (considered Day 0) and will be asked to take daily blood pressure reading. After one week of baseline readings, both arms will start their canagliflozin dosing protocols.

Participants will be asked to complete 7 total surveys to outline side effects and tolerability, one each day starting after their canagliflozin consumption.

Participants will be asked to complete a dietary intake journal through Day 0 – Day 14. Lifesum (<https://lifesum.com/>) should be used to track Carbohydrate/Protein/Fat consumption. Participants will share their dietary intake journal twice over their participation (Day 7 & Day 14).

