10.3 Safety and efficacy evaluations

The primary endpoint, average glucose, will be assessed by examining blood glucose (mg/dL) area under curve as measured by CGM. Glucose data on days without canagliflozin treatment will serve as a control.

The secondary endpoints of safety and tolerability and urinary glucose excretion will also be assessed. Safety and tolerability will be measured by adverse event reporting, blood pressure monitoring, and by comparing treatment tolerability survey results with control tolerability results through subjective surveys. Urinary glucose excretion will be measured by at-home glucose testing strips.

11 Investigational Product

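### The analysis of variance is named for different data in the Synopsis and Section 13, with no unit or participant term, and 10.3 leaves Arm B's control days open

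*Combined protocol and SAP*

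**What the plan says.** The Synopsis, under Statistical analysis, states "CGM readings will be analyzed using analysis of variance". Section 13 states "Blood tests will be analyzed using analysis of variance". Neither gives the unit (reading, day, period or participant), the factors, a participant term or an alpha level. The Synopsis efficacy criteria are CGM data and urinary glucose, and no blood test is scheduled in the available text.

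The endpoint and its comparison are set elsewhere. Section 10.3: "The primary endpoint, average glucose, will be assessed by examining blood glucose (mg/dL) area under curve as measured by CGM", followed by "Glucose data on days without canagliflozin treatment will serve as a control". Section 7.1 speaks of "studying baseline glucose levels with and without canagliflozin". Section 11.2 rules out placebo. The primary contrast is therefore within participant.

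On timing, Section 8.1 says "After one week of baseline readings, both arms will start their canagliflozin dosing protocols", and the Synopsis gives "Duration of treatment: 7 days". Arm A doses daily on Days 8-14. Arm B doses "every other day for a total of 4 doses" over the same days.

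**The concern.** Two analysts could each follow this text and reach different conclusions from the same data. Analysis of variance covers a repeated-measures model that respects the own-control design, and also an ordinary model that treats readings or days from one person as independent. The second kind misstates the error of the primary contrast. The direction depends on the unit chosen and on variances that nobody knows in advance, so a reader could not correct a published p-value afterwards.

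The control days raise a second open choice. The sentence in 10.3 would, taken literally, count Arm B's between-dose days as control. Any drug effect lasting into those days would dilute the contrast on which the third hypothesis in Section 6.4 (alternate-day use) depends. Left open, both choices could be made after the data are seen.

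**Working it through.** **No figure to reproduce.** The documents give up to 20 participants, 10 per arm, and no alpha, power, effect size or SD.

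**Inputs from the documents:** 20 participants; Days 1-7 before drug; Days 8-14 on the regimen.

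**Assumed inputs:** two-sided 5%; CGM data on Days 1-14; SDs in mg/dL of 5 or 8 between persons (s_b), 0 or 3 person-by-week (s_v), 3 or 5 between days (s_d), and 15 within day; 96 readings per day with first-order autocorrelation 0.8. This gives eight scenarios. The within-day part has variance 20.12 for a daily mean and 2.993 for a 7-day mean.

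**Closed form.** The true variance of the difference between the two period averages is V = 2(s_v² + s_d²/7 + 2.993)/20. An ordinary ANOVA instead uses approximately:
- readings (20 × 672 = 13,440 per period): 2(s_b² + s_v² + s_d² + 225)/13,440
- daily values (140 per period): 2(s_b² + s_v² + s_d² + 20.12)/140
- period means, unpaired: 2(s_b² + s_v² + s_d²/7 + 2.993)/20

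The false-positive rate is about 2Φ(−1.96·√(variance used / V)).

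Example 1 (s_b 5, s_v 3, s_d 3): V = 2(9 + 1.286 + 2.993)/20 = 1.328.
- Readings: 2 × 268/13,440 = 0.0399, rate about 73%.
- Daily: 2 × 63.12/140 = 0.902, rate about 11%.

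Example 2 (s_b 8, s_v 0, s_d 3): V = 2(1.286 + 2.993)/20 = 0.428.
- Readings: 2 × 298/13,440 = 0.0443, rate about 53%.
- Daily: 2 × 93.12/140 = 1.330, rate below 0.1% (simulated 0.2%, because the between-person variance varies from sample to sample).
- Unpaired means: 2 × 68.28/20 = 6.83, rate essentially 0.

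**Simulation, eight scenarios, no true effect:**

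| Analysis | Rejection at nominal 5% |
|---|---|
| Pooled readings | 54-75% |
| Daily values, no participant term | 0.2-11% |
| Daily values, participant block, day-level error | 4.9-5.3% if s_v = 0; 18-24% if s_v = 3 |
| Period means, unpaired | 0-0.4% |
| Period means, paired | 4.7-5.3% |
| Repeated-measures ANOVA on period means | 4.8-5.3% |

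A second set of assumptions (s_b 8, s_v 0 to 6, s_d 4; 24 or 96 readings per day with autocorrelation 0.65 or 0.9) gave 33-84% on readings, 0.6-18% on daily values, 0-0.5% on unpaired means and 4.3-5.8% paired.

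**Power lost without pairing.** For an assumed shift of 0.4 between-person SD, at within-participant correlations 0.5 / 0.7 / 0.8 / 0.9, a paired test on 20 participants has power 0.40 / 0.59 / 0.77 / 0.97. The unpaired ANOVA on the same means has 0.14 / 0.08 / 0.04 / 0.01.

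**Control days.** Four alternate-day doses within Days 8-14, with Day 15 placed 24 hours after the last, put Arm B's doses on Days 8, 10, 12 and 14. Literal 10.3 then gives Arm B 7 + 3 = 10 control days, of which Days 9, 11 and 13 (30%) lie between doses. If those days carry a fraction f of the dose-day effect:
- literal 10.3 contrast: 1 − 0.3f, or 100% down to 70% of the dose-day effect
- whole Days 8-14 against baseline: (4 + 3f)/7, or 57% up to 100%

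They are equal when 4 + 3f = 7 − 2.1f, so f = 3/5.1 = 0.59. The documents do not give f.

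**The case against.** The strongest reply is that this is brevity, not error. Repeated-measures ANOVA is analysis of variance, and the AUC endpoint in 10.3 argues against pooling single readings. The reference to blood tests may be loose wording for CGM glucose, which 10.3 itself describes as blood glucose. All of that stands. A reader might infer that the plan commits to an invalid analysis, or that it hides an unscheduled blood test. The text supports neither; it fails to exclude the wrong analysis.

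The error rates also rest on assumed variances. With a participant block and no person-by-week variation, even day-level error holds about 5%. This limits the size of the claim but not its direction: without a participant term, both sets of assumptions gave rates well away from 5% on readings and on unpaired means.

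A reader might also infer that reducing the data to one value per participant per period is enough. It is not: unpaired, those values give near 0% false positives and little power. The pairing restores the level.

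Finally, a reader might infer that literal 10.3 always shrinks Arm B's contrast more than a baseline-week control would. It does so only if f exceeds 0.59. Choosing the control days is partly a choice of estimand. The study design figure is not available, and it may settle the days. No section says when the sensor comes off; if it stayed on, Days 15-17 would also be days without drug.

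**Conclusion.** The point holds as under-specification with real consequences, and should be fixed before data are seen. The Synopsis and Section 13 name different data for the only inferential method, and neither reflects the within-participant primary contrast. An ordinary ANOVA, which the wording allows, would not hold its level, and the error runs from far too liberal on readings (the unit the Synopsis names) to far too conservative on unpaired means. The percentages are illustrations under assumed SDs, autocorrelation and reading frequency.

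The ambiguity over Arm B's Days 9, 11 and 13 follows from the text alone, subject to the missing figure. Sections 8.1 and the Synopsis point to the baseline week, while the literal wording of 10.3 does not. How much it matters depends on the unknown f.

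**What to change.** **Synopsis and Section 13.** State that CGM average glucose (AUC divided by hours recorded) is reduced to one value per participant per period and analysed within participant at two-sided alpha 0.05. Either a paired difference will do, or a repeated-measures ANOVA with period, arm, period-by-arm and participant terms, with period tested against the participant-by-period error. Name one primary test and give estimates with 95% confidence intervals for each arm. Testing overall, Arm A and Arm B each at 5% gave an 11-12% chance of at least one false positive in the simulation. Whether the primary test pools the arms or is by arm is the sponsor's choice, to be fixed before data are seen. Replace the reference to blood tests with the CGM endpoint, or say which tests are meant.

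**Section 10.3.** Make the pre-dose baseline week (Days 1-7, up to the first dose) the control in both arms. Report Arm B's dose days and between-dose days against it separately as well as together.

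**Cost.** Wording only; no new data. The paired SD is √(2(s_v² + s_d²/7 + 2.993)), which is 2.93 to 5.58 mg/dL under the assumed SDs. The 95% half-width is then 2.093 × SD/√20, or 1.4 to 2.6 mg/dL for all 20 participants (2.1 to 4.0 for one arm of 10), against about 0.4 from a reading-level ANOVA. Arm B's whole-week contrast averages dose and non-dose days and is smaller than the literal 10.3 contrast if f is below about 0.59. Drug effect remains confounded with calendar time, because both arms start drug after the same baseline week.
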